**Institutional Review Board
Intervention/Interaction Detailed Protocol**

Principal Investigator: [name], MPH

Project Title: An advance care planning intervention in the emergency department: a pilot randomized controlled trial

Version Date: 2021.12.07

For Intervention/Interaction studies, submit a Detailed Protocol that includes the following sections. If information in a particular section is not applicable, omit and include the other relevant information.

1. Background and Significance

- **Summarize relevant literature, data, and historical background**

Advance care planning (ACP) conversations can lead to well-informed shared decision making and improved quality of life at the end of life.¹ For seriously ill older adults, ACP conversations are associated with lower rates of in-hospital death, less aggressive medical care at the end of life, earlier hospice referrals, increased peacefulness, and a 56% greater likelihood to have end-of-life wishes known and followed.¹⁻⁸ Furthermore, patients with documented ACP conversations experience a 36% reduction in the cost of end-of-life care, with an average cost savings of \$1,041 per patient in the last week of life.⁹ Experts recognize that earlier ACP conversations are the key to “bend the cost curve” for health care.¹⁰ *Yet only 37% of seriously ill older adults have ACP conversations with their physicians,¹ on average 33 days before death.¹¹*

Emergency departments serve as an ideal setting to engage seriously ill yet clinically stable older adults who may benefit from ACP conversations. During the last six months of life, 75% of older adults visit the emergency department (ED).¹² ED visits are inflection points in these patients’ illness trajectories, signaling a more rapid rate of decline.¹³⁻¹⁵ More than 70% of these patients express priorities focused on comfort and quality of life rather than life extension,¹⁶ yet a systematic review revealed that 56% to 99% do not possess advance directives in the ED,¹⁷ and many are at risk of receiving care that does not align with their goals.¹⁸ *We propose to seize the opportunity of the ED visit to engage seriously ill older adults to initiate/reintroduce ACP conversations.*

ED clinicians lack practical methods to engage seriously ill older adults to engage in ACP conversations. ED clinicians recognize that an ED visit provides a time and location for seriously ill older adults to discuss ACP;¹⁹ however, the time-pressured ED environment discourages clinicians from conducting in-depth conversations.²⁰ *Practical methods to overcome these ED-specific barriers are needed to engage patients who may benefit from ACP conversations.*

- **Describe previous pre-clinical or clinical studies leading up to and supporting the proposed research**

In our prior research, we developed and piloted a ED clinician-led, behavioral intervention (*ED GOAL*) designed to engage seriously ill yet clinically stable older adults in the ED to address ACP with their outpatient clinicians.^{21,22} In an acceptability study, 82% (19/23 patients) found it acceptable and stated that it helped them engage in talking about their goals for future care with their outpatient clinicians.²¹ In a feasibility study (N=50), average patient-reported ACP self-efficacy increased from 3.8 to 4.3 on

a 5-point scale, new electronic medical record (EMR) documentation of ACP (new/change in health care proxy or advance directive forms) was found in 26% (13/50 patients), and new EMR documentation of ACP conversation (discussion of code status, health care proxy, or advance directive forms) was found in 40% (20/50 patients) of seriously ill older adults who underwent *ED GOAL* (under peer review). When COVID restrictions prevented us from conducting *ED GOAL* physically in the ED, we have demonstrated the feasibility of conducting our study virtually using phone/zoom (IRB Protocol 2020P002934, in preparation for publication).

- **Describe rationale behind the proposed research and significance to patients, society, and/or science**

Since the improvements in ACP engagement were seen in a one-arm, pre-/post-intervention feasibility study, we propose to test this in a pilot randomized clinical trial (RCT) as a next step. *ED GOAL* will facilitate ACP conversations for seriously ill older adults in or after leaving the ED. These findings will be used for a future R01 proposal to definitively test the efficacy of *ED GOAL* in a large multi-site pragmatic trial. We aim to establish *ED GOAL* as a national standard of care to help seriously ill older adults to receive care concordant with their goals.

2. Specific Aims and Objectives

- **Specify objectives and hypotheses to be tested in the research project**

Aim 1: Pilot test, in a randomized controlled design (N=120, 60 in each group), the effect of *ED GOAL* administered by trained nurses on patient and caregiver ACP engagement one month after leaving the ED.

Hypotheses: ACP engagement (a composite outcome combining patient-reported and EMR outcomes) will significantly increase in those who received *ED GOAL* compared to usual care.

Aim 2: Identify the patient-perceived benefits and obstacles of ACP conversations after *ED GOAL* using semi-structured interviews (N~30).

[figure not shown]
Rationale: Most patients who underwent our intervention in prior studies expressed their gratitude and reported how helpful the intervention was in their lives. Yet, these perceived benefits (“opened my eyes about what I need to focus in my life”) may be difficult to capture using validated, quantitative instruments. Furthermore, we will also elicit patient-perceived barriers to completing the ACP conversations.

3. General Description of Study Design

- **Explain the basic study design, e.g., parallel group, randomized controlled trial, open-label single arm study, cross over, adaptive, etc.**

This is a two-armed, parallel-design, pre-/post-intervention assessment study. We will conduct a randomized controlled trial for *ED GOAL* on a cohort of 120 older adults with serious illness to collect patient-centered outcomes and determine preliminary efficacy on increasing ACP engagement (self-reported and/or in the electronic medical record) one month after leaving the ED. We will also conduct qualitative interviews with participants of *ED GOAL*.

- **Provide study schema as applicable (a schema is required for greater than minimal risk studies, and optional for minimal risk studies)**

4. Subject Selection

Describe sources of subjects and procedures for subject selection, including the following:

- **Inclusion/Exclusion Criteria**

Participants will only consist of patients who meet the inclusion/exclusion criteria in **Table 1**. For eligible patients who have mild cognitive impairment (MCI) or mild dementia (as shown by cognitive impairment assessment), both the patient and the patient’s caregiver will be enrolled as subjects in the study. For patients with moderate to severe dementia, the caregivers will be the study participants, and no involvement of the patients will occur. We will determine the potential subject’s cognitive status by review of medical records and screening described in the “Subject Enrollment” section below.

The caregivers are defined as health care proxy or next of kin (when health care proxy has not been appointed). Patients without competency who has court-appointed legal guardians are excluded from this study given the nature of ACP conversations for this group is largely different from ordinary patient/caregivers. Given that this is a minimal risk study (i.e., patients and caregivers are routinely experiencing ACP conversations in their clinical encounters), we will obtain verbal consent/assent using the study information sheet.

Table 1 Patient eligibility criteria	
Inclusion	Exclusion
1. ≥50 years of age AND ≥1 Serious illness* OR ED clinician would not be surprised if patient died in the next 12 months (a validated prognostic sign) ^{23,24}	1. Acute physical or emotional distress
2. English-speaking	2. Determined by treating or study clinician not to be appropriate
3. Capacity to consent	3. Clearly documented goals for medical care** (Unless the treating or study clinician recommends that the intervention is clinically indicated)
a. Patient with mild cognitive impairment or mild dementia with capacity to consent (requires a caregiver/study partner to enroll)	4. Delirium (assessed using 3D-CAM)
b. Caregiver of patient with moderate/severe dementia with capacity to consent	5. Already enrolled in this study
	6. Unable/unwilling to schedule the follow-ups on the calendar

	7. Receive both the outpatient care for serious illness and primary care outside of the MGB system
*NYHA Stage III/IV congestive heart failure, chronic obstructive lung disease on home oxygen, chronic kidney disease on dialysis, or metastatic solid tumor cancer. In addition, patients with NYHA Stage I/II congestive heart failure, chronic obstructive lung disease not on home oxygen, chronic kidney disease not on dialysis will be included if recent hospitalization in the last 12 months exists.	**e.g., MOLST, medical order for life-sustaining treatment, documented serious illness conversations in clinician notes within the last 3 months, etc.

• **Local Recruitment Procedures:**

Explain in detail the methods and procedures you will use to recruit participants. Describe in a step-by-step procedure below:

- **How individuals are identified for recruitment including description of use of recruitment materials such as flyers, brochures, advertisements, letters, etc.**

Our research team will review the medical records in Epic to identify the potential subjects to approach in this study. To identify potential subjects in the ED, we will review the ED patient lists Monday to Friday between 8am to 6pm. To capture potential subjects we missed during this screening period, we will also review medical records of patients who visited the ED in the last 10 days so that we can enroll them virtually after leaving the ED/hospital (if admitted).

- **Who is responsible (role on research team) for identifying and recruiting individuals**

Trained RAs will search through the medical records to find potential subjects meeting our inclusion and exclusion criteria. The study clinician consenting the subjects will double check the eligibility criteria prior to consent.

- **When individuals are recruited**

Subjects will be approached for recruitment at the time of ED visit, during their hospitalization after the ED visit, or within 10 days of leaving the ED.

- **Where individuals are recruited**

We will recruit subjects in the ED, ED observation unit, or hospital floor at Brigham and Women’s Hospital, Massachusetts General Hospital, and Brigham and Women’s Faulkner Hospital.

We will make every attempt to enroll/approach the patient in the ED. We will follow the following steps:

1. When potential subjects are identified in the ED, clinical appropriateness is assessed with the treating clinicians;
2. The treating clinicians will introduce the study and obtain permission for our research team to approach the subject in the ED; and
3. The study team will contact the patient for eligibility assessment and consent (if eligible).

When in-person enrollment is not feasible due to COVID restrictions or logistical reasons (e.g., potential subjects are identified overnight when research team is not present), we will use the Patient Gateway recruitment strategy recommended by the IRB.

- **How recruitment goals match the prevalence rates of the condition/disease being studied and the populations most impacted by the condition/disease being studied**

Our recruitment goals match the target populations of clinicians who routinely conduct ACP conversations in their clinical practice.

- **Methods to enhance enrollment of diverse individuals and under-represented populations**

To comply with the NIH recommendations for clinical trials, once we approach 50% of enrollment target goals for each arm, we will begin to preferentially recruit minority and under-represented populations if they are <20% of the enrolled subjects to ensure that our study adequately represent the study population.

5. Subject Enrollment

- **Describe any pre-screening procedures as applicable. Indicate whether subjects will be prescreened over the phone and/or will be asked to provide separate informed consent specific to screening procedures.**

No pre-screening procedures are planned.

- **Describe in a step-by-step procedure the consent process including:**
 - **When and where informed consent will be obtained (including description of any electronic consenting procedures)**

Timing of consent:

The informed consent will be obtained at the time of ED visit, during the hospitalization, or after the potential subjects leave the ED in-person or over the phone/zoom. All study procedures including the consent process may occur in-person or over the phone/zoom depending on logistical restrictions (e.g., COVID surge restrictions) and patient/clinician preference.

Sound amplification device (if feasible):

Prior to the screening assessments, the study staff will offer a personal sound amplifier as a hearing-assistive device to subjects who may benefit from its use (e.g., subjects with hearing impairment issue). From our experience, given that the setting may be in the noisy ED, the subjects can experience difficulties answering our questions. Therefore, the hearing aids will help them respond to our prompts/instructions more appropriately.

Subject identification:

Trained RAs will use Epic to identify patients in the ED or the hospital 8am to 6pm Monday through Friday. To capture potential subjects that we may have missed, we will also review recent discharge list who might be eligible based on inclusion/exclusion criteria. Once a potential subject is identified, the trained RA will approach the treating clinician to see if the patient is eligible and have capacity to consent (if the potential subject is in the ED or in the hospital). The study procedure will pause whenever the study team is interrupted by clinical activities of the participants and resume when it is determined to be feasible again by the clinical team.

Enrollment procedures and cognitive impairment screening:

Our trained study clinician will review the eligibility criteria with the RA prior to engaging with the potential subject. If the potential subject is agreeable to learn more about our study verbally, the study clinician will administer a validated, delirium screening (3D-CAM).²⁵

If the patient is found to have no delirium, the study clinician will classify the patients based on known diagnosis of cognitive impairment or by administering a validated, cognitive impairment screening (MiniCog and/or Quick Dementia Rating System, QDRS).^{26,27} Depending on the cognitive impairment status, the patients and/or caregivers will be enrolled in the study (**Table 2**).

Table 2 Intervention target and outcome assessment		
Cognition status	Study participants	Outcome assessment
Normal (MiniCog >2 and/or QDRS 0-1)	Patient only	ACP engagement for patient + EMR
Mild cognitive impairment and mild dementia (MiniCog<3 and QDRS 2-12)	Patient and caregiver	ACP engagement for patient + ACP engagement for caregiver + EMR
Moderate and advanced dementia (MiniCog<3 and QDRS 13-30)	Caregiver only	ACP engagement for caregiver + EMR

Upon classification of patients by their cognitive status, informed consent will be obtained using a 4-item consent capacity checklist (see attached 4-item consent capacity checklist). For patients with known/documented moderate/severe dementia per medical record or self-report, we will approach the caregiver for enrollment and perform the 4-point consent capacity checklist. If the caregiver states that the patient can assent (e.g., verbal, able to comprehend, etc.), we will obtain an assent from the patient. Patients are not the subjects of this study.

At this time, the study clinician will announce to the subject that the research procedure will begin.

- **A separate description for adults and children if applicable**
Not applicable.
- **The process for obtaining consent from non-English speakers if applicable**
Not applicable.
- **The process to determine capacity to consent and use surrogate decision makers if applicable**

We will conduct the following procedures to determine the capacity to consent:

For subjects with no known diagnosis of mild cognitive impairment or dementia on medical record, we will ask the treating clinicians (if subjects are in the ED or in the hospital) regarding their assessment of capacity to consent and clinical stability to approach the subject. Then, the study clinician will follow the procedures described above to classify the patients based on cognitive impairment status and use the 4-item capacity checklist for consent.

For subjects with a known diagnosis of mild cognitive impairment or mild dementia, we will ask the treating clinicians (if subjects are in the ED or in the hospital) regarding their assessment of capacity to consent and clinical stability to approach the subject. At the same time, we will confirm the availability of a caregiver to serve as a study partner. If caregiver is unavailable, the subject will be excluded. Then, the study clinician will follow the procedures described above to classify the patients based on cognitive impairment status and use the 4-item capacity checklist for consent.

For subjects with a known diagnosis of moderate to advanced dementia, the caregivers will be consented for the study (patients will not be the subjects of our study). We will use the 4-item consent capacity checklist.

- **Procedures to minimize undue influence to enroll, particularly if recruiting the investigators' own patients**
The study team will have no patient/clinician relationship with the potential subjects being approached in this study.

- **Describe post-consent intervention assignment and randomization method if applicable**

We will have three groups of participants based on cognitive ability for this study:

- 1) Patients with normal cognition
- 2) Patients with MCI or mild dementia + their caregivers (both are participants)
- 3) Caregivers of patients with moderate and advanced dementia (only the caregivers are the participants)

Upon classification of eligible participants into the correct group above, we will randomly assign them into one of two arms of the study using block randomization of four using a computer-generated algorithm:

- 1) Intervention (*ED GOAL*)
- 2) Control (usual care)

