6. STUDY PROCEDURES

Provide detailed description of all study visits, procedures, and data collections, including:

- **Description of each study visit and procedures at each visit (include a schedule/table of study procedures)**

Initial enrollment (~30 to 60 minutes total):

After the consent, our trained study clinician will administer the intervention to the participant in-person, on the phone, or over zoom depending on participant preference. After the intervention is completed, the RA will obtain post-enrollment questionnaires and also schedule dates/times for the follow-up appointments. With participants' permission, the study clinician will document the clinically important findings elicited from the participant (e.g., preferences for end-of-life care goals) in Epic's ACP module and also send an email regarding the findings to patient's outpatient clinicians within Mass General Brigham health system via secure email. The study team will also provide the post-enrollment patient handout (see attachment) to the participants. All participants in the intervention arm will receive the same intervention and follow-up procedures.

Follow-up appointments (~30 to 45 minutes each):

During the scheduled follow-up appointments on the phone/zoom, our RA will administer surveys to assess for the outcomes. In addition, if the participants report that they have not had conversations with their outpatient clinicians about ACP, our study clinician will conduct brief coaching to overcome the obstacles participants might be facing in this process and also document clinically relevant information in Epic to notify to the outpatient clinician.

Table 3 Study visits		
Study visit	Intervention	Outcome assessment
Initial enrollment	ED GOAL	Post-enrollment survey

1-month follow-up	ACP navigation coaching (as needed)	Follow-up patient-reported outcomes surveys
3-month follow-up	ACP navigation coaching (as needed)	Follow-up patient-reported outcomes surveys
6-month follow-up	ACP navigation coaching (as needed)	Follow-up patient-reported outcomes surveys

- **Description of study drugs, devices, or other interventions/exposures administered, including:**

- **Dose, method of administration, schedule of administration, dose modifications**

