EMR documentation (primary outcome)	Review EMR to see if new documentation of ACP conversation, change in code status, or advance directive forms documented by physicians or mid-level providers exist.	Baseline & at 1, 6, and 12 months
Self-reported ACP conversation survey (primary outcome)	Quantitative and qualitative questionnaires to assess the self-reported completion of ACP conversations with outpatient clinicians and families as well as barriers/facilitators of this process.	At 1, 3, and 6 months

Heard and understood survey (secondary outcome)	A validated instrument for seriously ill patients to report how well they feel heard and understood about their wishes for end-of-life care. ³¹	Baseline & 1, 3, and 6 months
Quality of communication survey (secondary outcome)	A validated instrument to measure the quality of communication about end-of-life care. ³²	Baseline & at 1, 3, and 6 months
Healthcare utilization (secondary outcomes)	Review EMR to see # of urgent care visits, ED visits, hospitalizations, hospice visits, and outpatient visits.	At 6 and 12 months before and 1, 6, 12 months after enrollment
Mortality	Review EMR to determine patient's vital status.	At 1, 3, and 6 months
Qualitative benefits and obstacles of ACP conversations after ED GOAL (secondary outcome)	Semi-structured interviews to assess the benefits of ED GOAL and obstacles participants faced in completing more ACP conversations with their outpatient clinicians and loved ones after ED GOAL (see interview guide).	At 1, 3, and/or 6 months

- **Description of planned genetic research as applicable (e.g., specific description of whole genome sequencing, creation of immortalized cell lines or induced pluripotent stems cells, and sharing of genetic material with collaborators and central repositories as applicable, etc.)**
Not applicable.
- **Description of plans for return of research results as applicable (e.g., specific description of, rationale for, and process by which research results will be returned, including to whom, by whom, and when, etc.). Include plans for managing incidental findings as applicable.**
Not applicable.
- **Definition of primary and secondary outcomes/endpoints. Note that outcome measures should be quantifiable and measurable.**
Please see **Table 4** above.
- **Definition of study termination criteria, e.g., objective criteria for clinical worsening, lack of improvement, and/or unacceptable adverse events**

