Describe plans for statistical analysis, including:

- **Statistical methods/data analysis plan**

Aim 1 quantitative data analysis:

We will conduct an intention-to-treat analysis. Since the primary outcome is mean change in self-reported ACP engagement, we do not expect differences among patients who are admitted vs. discharged. For our secondary outcome, we suspect that there is a propensity of more ACP documentation in patients who are hospitalized and missingness in patients who are primarily cared for at outside institutions. We will plan to use regression in subgroup analysis for ACP documentation to account for hospitalization status. In addition, we will perform sensitivity analyses to account for clustering by individual outpatient clinicians, palliative care consultations, and cognitive impairment status. We will also perform sensitivity analyses for survey respondents (e.g., patients vs. caregivers). We will compare patient demographics by study arm to assess randomization using bivariable analyses (t-test for continuous variables and chi-square for categorical variables). The mean changes in ACP engagement (primary outcome) at one month will be compared by study arms to estimate effect sizes. Within arms, we will use a one-sample binomial exact test of proportions for categorical outcomes (e.g., EMR documentation), and Wilcoxon signed ranks test for ordinal outcomes (e.g., ACP Engagement Survey) at baseline, after the intervention at one month. A p-value of 0.05 will be the significance threshold. To address missing data, I will conduct a secondary analysis using linear mixed models at baseline and one month. For qualitative outcomes,

Aim 2 qualitative data analysis:

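### Exclusion 7 keeps patients with one kind of care outside MGB, and no planned analysis deals with the EMR records that may be missed for them

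*Combined protocol and SAP*

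**What the plan says.** **Eligibility (section 4, Table 1, exclusion 7).** A patient is excluded if they "Receive both the outpatient care for serious illness and primary care outside of the MGB system". Both conditions must be met.

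**Outcome sources (section 6, measures table).** The EMR documentation outcome is "Review EMR to see if new documentation of ACP conversation, change in code status, or advance directive forms" entered by doctors or mid-level clinicians. Utilization is "Review EMR to see # of urgent care visits, ED visits, hospitalizations, hospice visits, and outpatient visits". No retrieval of outside records is described for either. A separate survey, at 1, 3 and 6 months, asks about "self-reported completion of ACP conversations with outpatient clinicians and families" and is not limited to MGB clinicians.

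**Intervention (section 6, initial enrollment).** With permission, the study clinician enters the findings in Epic and e-mails them to the patient's "outpatient clinicians within Mass General Brigham health system".

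**Analysis (section 9, Aim 1).** For ACP documentation the plan foresees "missingness in patients who are primarily cared for at outside institutions". The remedy that follows is: "We will plan to use regression in subgroup analysis for ACP documentation to account for hospitalization status". The sensitivity analyses listed concern clustering by outpatient clinician, palliative care consultation, cognitive impairment and type of respondent. Missing data are addressed by a secondary linear mixed model at baseline and one month.

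**The concern.** A patient may have an oncologist or dialysis team outside MGB and primary care inside it, or the reverse. That patient is eligible. If the outside clinician holds and documents an ACP conversation, the EMR review may not find it. Visits to the outside provider may likewise be left out of the utilization counts.

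The difficulty is how such a gap enters the data. A search for whether new documentation is present, or a count of visits, returns no or zero when nothing is found, unless a rule says otherwise. The plan has no such rule. A missing-data method works on values flagged as missing, so it cannot recognise a recorded no that is false.

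The pilot's stated purpose is to estimate preliminary effect sizes for a larger trial. An EMR documentation difference affected by incomplete capture would be carried into that planning with nothing in the analysis to show how large the effect of capture might be.

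**Working it through.** The plan gives no figure for the share of partly outside patients or for how much of their care the EMR captures, so there is nothing of its own to reproduce. Its 90% power statement does not involve care location and is not used here.

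**Step 1. Who stays in.**

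| Primary care | Serious-illness care | Exclusion 7 |
|---|---|---|
| MGB | MGB | kept |
| MGB | outside | kept |
| outside | MGB | kept |
| outside | outside | excluded |

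Since the last row is removed, the missingness that section 9 expects must come chiefly from the two middle rows.

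**Step 2. Which outcomes are exposed.**

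| Outcome | Source | Exposed? |
|---|---|---|
| New ACP documentation | EMR review | yes |
| Healthcare utilization | EMR review | yes, with no second source |
| Change in self-reported ACP engagement | survey | no |
| Self-reported conversation | survey, no MGB limit | no |

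**Step 3. Which planned analyses use care location.** None: not the hospitalization regression, the four sensitivity analyses or the mixed model. The measures table lists no baseline field for it. Section 9 raises the missingness for documentation only; it does not mention it for utilization.

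**Step 4. Size if capture is equal in both arms.** Let f be the share of patients partly outside and s the fraction of their ACP documentation that reaches the record reviewed. Then

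observed difference = full-capture difference × (1 − f(1 − s)).

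Assumptions: full-capture rates of 20% (control) and 40% (ED GOAL), a 20-point difference, with f from 10% to 30%. The 40% borrows the feasibility study's 20/50 in section 1. That is an observed EMR rate and may already include some under-capture, so it serves only as an example.

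- Half captured (s = 0.5): 20 × (1 − 0.10 × 0.5) = 19 points; 20 × (1 − 0.30 × 0.5) = 17 points.
- None captured (s = 0): 20 × (1 − 0.10) = 18 points; 20 × (1 − 0.30) = 14 points.

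**Step 5. If capture differs by arm.** With separate capture rates,

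observed difference = 40 × (1 − f(1 − s_T)) − 20 × (1 − f(1 − s_C)).

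At f = 30%:

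- s_T = 0.5, s_C = 0: 40 × 0.85 − 20 × 0.70 = 34 − 14 = 20 points, no dilution.
- s_T = 0, s_C = 0.5: 40 × 0.70 − 20 × 0.85 = 28 − 17 = 11 points.

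Under these rates the difference is exaggerated once s_T exceeds (1 + s_C)/2. The sign of the error therefore depends on quantities that the plan does not give.

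**Step 6. Scale against sampling error.** The 95% half-width at 20% v 40% is 1.96 × √((0.20 × 0.80 + 0.40 × 0.60)/n) = 1.96 × √(0.40/n).

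- All randomised, n = 60 per arm: 16.0 points.
- Both in MGB, f = 10%, n = 60 × 0.90 = 54: 16.9 points.
- Both in MGB, f = 30%, n = 60 × 0.70 = 42: 19.1 points.

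**The case against.** The case on the other side is substantial, and most of it stands as a limit on the point.

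- **Coding.** A reader might infer that outside conversations and visits are scored as not having happened. No section says so. Section 9 calls the problem missingness, and the measures table does not restrict the review to notes written at MGB. The default to no or zero is what an unqualified search or count would produce; it is not a stated rule.
- **Self-report.** Conversations with outside clinicians can be captured by the survey, which the measures table lists as a primary outcome. Section 9 names self-reported engagement change as primary, and care location does not affect its measurement. Section 2 and the measures table give EMR documentation a primary role while section 9 makes it secondary. That is a separate matter, but the point bears only on the EMR part.
- **The remaining MGB clinician.** A reader might infer that the EMR outcome cannot show an effect in these patients. It can. Each of them still has one kind of care inside MGB, where the clinician can receive the e-mail, hold the conversation and document it, and inpatient documentation also counts. Zero capture is therefore an extreme bound.
- **Direction.** A reader might infer that the pilot is bound to pass on too small an effect. The Epic entry and the e-mail follow the intervention, so capture may differ by arm.
- **Relevance.** The half-capture loss of 1 to 3 points is small beside a half-width of 16 points in a pilot that section 9 says is not powered. If the later multi-site trial also uses EMR review, the all-randomised difference is itself a useful planning input.

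These arguments do not supply the missing analysis. The plan names an ascertainment problem and then adjusts for something else, and utilization has no second source.

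**Conclusion.** The point holds in limited form. Exclusion 7 admits patients with one kind of care outside MGB. The two EMR-derived outcomes may miss what happens at the outside provider, and no planned analysis uses care location. The self-reported engagement change and the self-reported conversation survey are not affected.

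With equal capture, the EMR documentation difference shrinks in proportion to the uncaptured share: from 20 points to 19 to 17 with half captured, and to 18 to 14 at the zero-capture bound. These figures rest on an assumed 10% to 30% share and an assumed 20-point difference. If capture differs by arm, the error may be larger, absent or reversed. The documents do not support a firm claim that outside events are scored as absent, or that the pilot's effect size will be too small. This is an inexpensive improvement worth making to the EMR analyses; it is not a fault in the eligibility rule itself.

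**What to change.** Keep eligibility as it is.

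1. Before randomisation, record two fields: whether primary care is within MGB, and whether serious-illness care is within MGB.
2. For EMR documentation and utilization, pre-specify a between-arm sensitivity estimate in participants with both kinds of care in MGB, reported beside the all-randomised estimate. Because the fields are fixed before allocation, the restricted comparison is still between randomised groups.
3. For participants with either kind of care outside, report the self-reported conversation alongside the EMR result. Do not read an absent record as proof that no conversation took place, and state in the plan how a search that finds nothing is coded.

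The cost is two baseline fields and one added analysis. Most of the information is looked up for exclusion 7 anyway, although once one kind of care is found inside MGB, staff must still check the other. The restricted estimate uses fewer patients and is less precise (half-width 16.9 to 19.1 points against 16.0 in the example), and it describes a narrower population. It also reduces the gap without closing it, since a patient with both kinds of care in MGB can still be seen elsewhere. It should therefore accompany the all-randomised estimate and not replace it.
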